10.2 Handling of Multiplicity

No adjustment for multiple comparisons is used in this open-label single-arm study.

10.3 Primary Efficacy Analysis

The primary efficacy endpoint is SVR_{12} (HCV RNA < LLOQ 12 weeks after the last actual dose of study drug) in the ITT population. The number and percentage of subjects in the ITT population achieving SVR_{12} will be summarized with a two-sided 95% confidence interval, calculated using the normal approximation to the binomial distribution. If the SVR_{12} rate is 100%, then the Wilson's score method will be used to calculate the confidence interval.

The lower confidence bound of the 2-sided 95% CI (LCB) for the percentage of subjects achieving SVR_{12} must exceed 86% to achieve non-inferiority to the standard of care.

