8.1.2.1 Primary Efficacy Endpoints

The primary efficacy endpoint is SVR_{12} (HCV RNA < LLOQ 12 weeks after the last actual dose of study drug) in the ITT population. The number and percentage of subjects in the ITT population achieving SVR_{12} will be summarized with a two-sided 95% confidence interval, calculated using the normal approximation to the binomial distribution. If the SVR_{12} rate is 100%, then the Wilson's score method will be used to calculate the confidence interval.

The lower confidence bound of the 2-sided 95% CI (LCB) for the percentage of subjects achieving SVR₁₂ must exceed 86% to achieve non-inferiority to the standard of care.

[figure not shown]

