8.2 Determination of Sample Size

It is planned to enroll approximately 90 subjects with a minimum of 15 post-renal transplant subjects and a maximum of approximately 50 subjects with HCV genotype 1 infection. The primary efficacy endpoint of SVR₁₂ will be assessed for the ITT population. For the primary efficacy endpoint of SVR₁₂, with a sample size of 90 subjects and assuming that 96% of the subjects will achieve SVR₁₂, this study has greater than 90% power to show non-inferiority to the historical SVR₁₂ rate of 94% (based on the lower bound of a normal approximation of a single binomial proportion confidence interval being above a threshold of 86%) using a one-sample test for superiority using EAST 6.3.

No adjustment for dropouts is applicable because subjects who do not have data at Post-Treatment Week 12 (after imputing) are counted as failures for SVR₁₂.

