4.3 Sample Size

It is planned to enroll approximately 90 subjects with a minimum of 15 post-renal transplant subjects and a maximum of approximately 50 subjects with HCV genotype 1 infection in this study. The primary efficacy endpoint of SVR₁₂ will be assessed for the ITT population. For the primary efficacy endpoint of SVR₁₂, with a sample size of 90 subjects and assuming that 96% of the subjects will achieve SVR₁₂, this study has

greater than 90% power to show non-inferiority to the historical SVR_{12} rate of 94% (based on the lower bound of a normal approximation of a single binomial proportion confidence interval being above a threshold of 86%) using a one-sample test for superiority using EAST 6.3.

The 86% threshold was established by applying an 8% non-inferiority margin to the historical SVR₁₂ rate of 94%

No adjustment for dropouts is applicable because subjects who do not have data at Post-Treatment Week 12 (after imputing) are counted as failures for SVR_{12} .

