10.5 Sensitivity Analyses for SVR

The following analysis approaches will be used as sensitivity analyses for the SVR₁₂ rate.

- A two-sided 95% confidence interval for the SVR₁₂ rate in the ITT population will be calculated using a Wilson score interval.
- The SVR₁₂ rate in the mITT-GT and mITT-GT-VF populations, as applicable, will be calculated, as well as the corresponding two-sided 95% confidence interval using a Wilson score interval and a Normal approximation to the binomial distribution.

Listings of subjects excluded from the mITT-GT and mITT-GT-VF populations will be provided, as applicable.

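### At 90 subjects the primary non-inferiority rule, based on a normal-approximation bound, has an exact one-sided error of 5.3%, about twice the 2.5% that the plan implies

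*SAP*

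**What the plan says.** SAP 10.3 summarises SVR12 in the ITT population with a "two-sided 95% confidence interval, calculated using the normal approximation to the binomial distribution". Protocol 8.1.2.1 and the synopsis say the same. The lower limit "must exceed 86% to achieve non-inferiority to the standard of care". There is one exception: if the observed rate is 100%, "then the Wilson's score method will be used to calculate the confidence interval" (SAP 10.3).

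Protocol 8.1 sets all tests and intervals at a two-sided alpha of 0.05. The 86% threshold is a historical 94% minus an 8-point margin (Protocol 8.2.1, SAP 4.3). For about 90 subjects, and "assuming that 96% of the subjects will achieve SVR₁₂", Protocol 8.2 states that "this study has greater than 90% power to show non-inferiority".

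Under SAP 10.5 a second 95% interval for the same ITT rate "will be calculated using a Wilson score interval", as a sensitivity analysis. Protocol 8.1.2.3 agrees. Neither document gives that result any part in the decision, and neither reports the actual error rate of the primary rule.

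**The concern.** The normal-approximation (Wald) interval takes its standard error from the observed rate. Near 100% that standard error is small, so the lower limit sits too high. This trial expects a rate of about 96% in about 90 subjects, which is where the approximation is weak.

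Only the lower limit decides, so a limit that is too high leads directly to false claims of non-inferiority. There is no concurrent control, and Protocol 8.2.1 describes the margin as already somewhat wider than in the sponsor's other studies. SAP 4.4 plans the result for regulatory submissions. Elsewhere in the efficacy plan Wilson intervals are standard: for the secondary endpoints, the subgroups and the additional SVR and relapse endpoints (Protocol 8.1.2.2, 8.1.2.4 and 8.1.2.5; SAP 10.4, 10.6 and 10.7). The documents do not explain why the one analysis that carries a claim is treated differently.

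**Working it through.** **Inputs.** n = 90, true rate under the design 96%, threshold 86% (Protocol 8.2, SAP 4.3). Two-sided alpha 0.05 (Protocol 8.1), so z = 1.96. The one-sided 2.5% is derived from this; the documents do not state it.

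**1. The plan's own power.** The documents do not name the variance used, so both normal formulas were tried.
- Alternative variance: SE = √(0.96 × 0.04 / 90) = 0.02066. Power = Φ(0.10 / 0.02066 − 1.96) = 99.8%.
- Null variance: SE₀ = √(0.86 × 0.14 / 90) = 0.03658. Power = Φ((0.10 − 1.96 × 0.03658) / 0.02066) = 91.5%.
- Exact binomial power of the planned rule (cut-off from step 2): P(X ≥ 83 | 90, 0.96) = 97.2%.

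All exceed 90%, so the stated figure reproduces.

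**2. Cut-off of the planned rule.** Lower limit = p − 1.96 √(p(1 − p)/n).
- 82/90: 0.9111 − 1.96 × 0.0300 = 85.23%, fails.
- 83/90: 0.9222 − 1.96 × 0.0282 = 86.69%, passes.

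For the same 83/90 the Wilson lower limit is 84.81% and the Clopper-Pearson limit 84.63%. Both fail.

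**3. Error of the planned rule.** P(X ≥ 83 | 90, 0.86) = 5.31%, and 5.31 / 2.5 = 2.1.

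**4. The Wilson rule.** Lower limit = [p + z²/2n − z √(p(1 − p)/n + z²/4n²)] / (1 + z²/n).
- 84/90: (0.9333 + 0.0213 − 0.0558) / 1.0427 = 86.21%, passes.
- Error: P(X ≥ 84 | 90, 0.86) = 2.42%.
- Power at 96%: P(X ≥ 84 | 90, 0.96) = 93.1%.

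Clopper-Pearson gives the same cut-off at n = 90 (84/90, lower limit 86.05%).

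**5. Other sample sizes.** Enrolment is only approximately 90, so every N from 85 to 100 was computed. Selected rows (error at a true 86%, power at a true 96%):

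| N | Planned: cut-off | error | power | Wilson: cut-off | error | power |
|---|---|---|---|---|---|---|
| 85 | 79 | 3.75% | 94.6% | 80 | 1.54% | 87.5% |
| 86 | 79 | 7.23% | 97.8% | 81 | 1.40% | 87.0% |
| 88 | 81 | 6.20% | 97.5% | 83 | 1.15% | 85.9% |
| 89 | 82 | 5.74% | 97.4% | 83 | 2.65% | 93.4% |
| 90 | 83 | 5.31% | 97.2% | 84 | 2.42% | 93.1% |
| 95 | 88 | 3.55% | 96.3% | 89 | 1.54% | 91.3% |
| 96 | 88 | 6.64% | 98.5% | 90 | 1.41% | 91.0% |
| 99 | 91 | 5.31% | 98.2% | 92 | 2.54% | 95.5% |

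Over the whole range the planned rule's error runs from 3.6% (N = 95) to 7.2% (N = 86). The Wilson error runs from 1.2% to 2.7%, and its power is above 90% for every N from 89 to 100.

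**6. Where the rules differ.** At n = 90 they differ only at exactly 83 responders. The probability of that count is 5.31 − 2.42 = 2.9% at a true 86%, 82.8 − 70.5 = 12.3% at 94%, and 97.2 − 93.1 = 4.1% at 96%. At N = 86 to 88 and 96 to 98 they differ at two counts.

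**The case against.** The best defence is that the reach is narrow. At n = 90 one outcome separates the rules, and it has a 4.1% probability at the planned rate. The method is prespecified, the two documents agree on it, and the planned Wilson interval would reveal a conflict. All of that is true. But the conflict would be visible without being resolved, because the sensitivity result does not enter the decision. And that single outcome accounts for the error rising from 2.42% to 5.31%.

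The 2.5% benchmark is also inferred. That stands, and it should be labelled as derived. The inference is the usual one when only the lower limit of a two-sided 95% interval decides.

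A reader might go further and infer three things that the documents and the arithmetic do not support:

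- *That the power statement is wrong.* It reproduces under every formula tried.
- *That poor coverage near 96% endangers the claim.* At a true 96% the planned interval covers 90.2% of the time, and its lower limit lies above the truth with probability 9.5%. All of that 9.5% comes from 89/90, which passes under either rule. Likewise, the lower limit drops from 96.7% at 89/90 (Wald) to 95.9% at 90/90 (Wilson), and upper limits exceed 100% from 87/90 to 89/90. These are untidy but change no decision.
- *That Wilson guarantees at most 2.5% error and more than 90% power at any size.* It does not: see N = 89 and 99 for the error and N = 85 to 88 for the power.

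**Conclusion.** The concern holds as a defect in the error rate of the decision rule. At n = 90 the chance of declaring non-inferiority at a true 86% is 5.31%, against a derived one-sided 2.5%. The excess is present at every N from 85 to 100. Nothing elsewhere in the protocol or SAP corrects it.

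The result rests on independent binomial outcomes, a denominator of all treated subjects with missing data counted as failures after imputation (as planned), and 86% taken as the null value. It does not depend on a preference for Wilson, since the exact interval gives the same pass mark at n = 90. The practical effect is limited to results at the pass mark, but there the plan would declare success on data that its own sensitivity interval does not support.

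**What to change.** In SAP 10.3, Protocol 8.1.2.1 and the synopsis, make the two-sided 95% Wilson score interval the primary interval at every observed rate and drop the 100% exception. Declare non-inferiority if its lower limit exceeds 86%. Move the normal-approximation interval to the sensitivity analyses (SAP 10.5, Protocol 8.1.2.3). In Protocol 8.2 and SAP 4.3, state the power for the Wilson rule: 93.1% (exact) at n = 90 and a true 96%. Make the change before the primary-analysis lock.

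The work is wording only, since both intervals are already specified for this rate. The statistical costs should be accepted openly:

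- The pass mark rises by one responder at n = 90, and by two at N = 86 to 88 and 96 to 98.
- Power at a true 96% is 86% to 87.5% if only 85 to 88 subjects are treated, so the power claim needs at least 89.
- If the true rate is only the historical 94%, power at n = 90 falls from 82.8% to 70.5%.
- The error still slightly exceeds 2.5% at N = 89 (2.65%) and N = 99 (2.54%).

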10.4 Secondary Efficacy Analyses

Two secondary efficacy endpoints will be summarized:

• the percentage of subjects with on-treatment virologic failure (defined as **On-treatment virologic failure**);

• the percentage of subjects with post-treatment relapse (defined as **Relapse**₁₂; subjects with reinfection will be summarized separately).

The number and percentage of subjects with on-treatment virologic failure and post-treatment relapse (**Relapse**₁₂) will be summarized with two-sided 95% Wilson score intervals.

In addition, a summary of reasons for SVR_{12} non-response (e.g., on-treatment virologic failure, relapse, other) will be provided.

10.5 Sensitivity Analyses for SVR

The following analysis approaches will be used as sensitivity analyses for the SVR₁₂ rate.

- A two-sided 95% confidence interval for the SVR₁₂ rate in the ITT population will be calculated using a Wilson score interval.
- The SVR₁₂ rate in the mITT-GT and mITT-GT-VF populations, as applicable, will be calculated, as well as the corresponding two-sided 95% confidence interval using a Wilson score interval and a Normal approximation to the binomial distribution.

Listings of subjects excluded from the mITT-GT and mITT-GT-VF populations will be provided, as applicable.

10.5.1 Imputation Approaches

In addition to imputing SVR_{12} as described in Section 6.3, SVR_{12} will be presented using the following other methods to impute missing HCV RNA values:

- imputing any missing HCV RNA values in the SVR₁₂ window by carrying forward the last non-missing (post-baseline) HCV RNA value prior to the SVR₁₂ window.
- impute as described in Section 6.3 but treat SVR₁₂ non-responders who were categorized as "prematurely discontinued study drug with no on-treatment

virologic failure" or "missing follow-up data in the SVR_{12} window" as successes.

For each of these, the percentage of subjects with SVR₁₂ will be presented along with two-sided 95% Normal and Wilson score confidence intervals.

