 $SVR_{12} = HCV RNA < LLOQ$ in the SVR_{12} window (12 weeks after the last actual dose of study drug) without any confirmed quantifiable ($\geq LLOQ$) post-treatment value before or during that SVR window.

 $SVR_{24} = HCV RNA < LLOQ$ in the SVR_{24} window (24 weeks after the last actual dose of study drug) without any confirmed quantifiable ($\geq LLOQ$) post-treatment value before or during that SVR window.

Relapse₁₂ = confirmed HCV RNA \geq LLOQ between end of treatment and 12 weeks after last actual dose of study drug (up to and including the SVR₁₂ assessment time point) for a subject with HCV RNA < LLOQ at Final Treatment Visit who completed treatment (defined as study drug duration \geq 77 days), excluding reinfection as described below.

Relapse₂₄ = confirmed HCV RNA \geq LLOQ within the SVR₂₄ window for a subject who achieved SVR₁₂ and has HCV RNA data available in the SVR₂₄ window, excluding reinfection.

Relapse_{overall} = confirmed HCV RNA \geq LLOQ between end of treatment and up to and including the last HCV RNA measurement collected in the PT Period for a subject with HCV RNA < LLOQ at Final Treatment Visit who completed treatment (defined as study drug duration \geq 77 days), excluding reinfection.

Virologic failure = On-treatment virologic failure or Relapse_{overall}.

Only subjects who have at least one post-treatment HCV RNA value will be included in analyses of relapse. For the analysis of relapse, completion of treatment is defined as any subject with study drug duration of 77 days or greater. If the last available post-treatment value is \geq LLOQ, then the subject will be considered a relapse (i.e., will not require confirmation).

HCV reinfection is defined as confirmed HCV RNA \geq LLOQ after the end of treatment in a subject who had HCV RNA < LLOQ at Final Treatment Visit, along with the post treatment detection of a different HCV genotype, subtype, or clade compared with baseline, as determined by phylogenetic analysis of the NS3 or NS5A, and/or NS5B gene sequences. Reinfection in the case of the same HCV subtype is defined as a clade switch, as indicated by the lack of clustering between the baseline and post-treatment sequences by phylogenetic analysis. If phylogenetic analysis is not possible due to technical difficulties, HCV reinfection may be determined with a confirmed HCV genotype or subgenotype switch by the Versant HCV Genotype Inno-LiPA Assay v2.0 or Sanger assay.

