Post-treatment relapse is defined as described earlier (**Relapse**₁₂, **Relapse**₂₄, **Relapse**_{overall}), and no genotype, subtype, or clade switch compared with baseline as determined by phylogenetic analysis of the NS3 or NS5A gene sequences. If phylogenetic analysis is not possible due to technical difficulties, the subject will be defined as having a post-treatment relapse unless an HCV genotype or subgenotype switch is confirmed by the Versant HCV Genotype Inno-LiPA Assay v2.0 or Sanger assay.

Reasons for SVR₁₂ Non-Response

Subjects who do not achieve SVR₁₂ (SVR₁₂ non-responders) will be categorized as having:

- 1. On-treatment virologic failure (see **On-treatment virologic failure** definition);
- Relapse (defined according to the Relapse₁₂ definition for subjects who complete treatment);
- Prematurely discontinued study drug with no on-treatment virologic failure (defined as any SVR₁₂ non-responder who prematurely discontinued study drug [study drug duration < 77 days] and did not meet the **On-treatment virologic** failure definition);
- 4. HCV reinfection (see definition described earlier);
- 5. Missing follow-up data in the SVR₁₂ window (defined as any subject who completed study drug without data in the SVR₁₂ window after applying the imputation rules and not meeting the definitions of [1], [2], [3], or [4]);
- Other (defined as any SVR₁₂ non-responder not meeting the definitions of [1] [5]).

Reasons for SVR24 Non-Response

Subjects who do not achieve SVR₂₄ (SVR₂₄ non-responders) will be categorized as having:

- 1. On-treatment virologic failure (see **On-treatment virologic failure** definition);
- Relapse (defined according to the Relapse₁₂ definition for subjects who complete treatment);
- 3. Relapsed after achieving SVR₁₂ (see **Relapse₂₄** definition);
- 4. Prematurely discontinued study drug with no on-treatment virologic failure (defined as any SVR₂₄ non-responder who prematurely discontinued study drug

[study drug duration < 77 days] and did not meet the **On-treatment virologic** failure, Relapse₁₂, or Relapse₂₄ definitions);

- 5. HCV reinfection;
- 6. Missing follow-up data in the SVR₂₄ window (defined as any subject who completed study drug without data in the SVR₂₄ window after applying the imputation rules and not meeting the definitions of [1], [2], [3], [4], or [5]);
- Other (defined as any SVR₂₄ non-responder not meeting the definitions of [1] [6]).

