10.7 Additional Efficacy Analyses

The following additional efficacy endpoints will be summarized:

- The percentage of subjects with HCV RNA < LLOQ at each post-baseline visit in the Treatment Period (using data as observed);
- The percentage of DAA-naïve subjects with on-treatment virologic failure;
- The percentage of DAA-naïve subjects with post-treatment relapse;
- The percentage of subjects with SVR₄;
- The percentage of subjects with SVR₂₄;

- The percentage of subjects who relapsed after achieving SVR₁₂ (**Relapse₂₄**);
- The percentage of subjects with virologic failure through Post-Treatment Week 12 (i.e., the SVR₁₂ non-responders due to on-treatment virologic failure or Relapse₁₂)

In the above analyses for SVR, virologic failure, and relapse, the percentage of subjects with a two-sided 95% Wilson score interval will be summarized. Imputations for missing data will be performed as described in Section 6.3 for analysis of SVR, where a missing response will be imputed as a failure after performing the described imputation. All other endpoints will be presented using data as observed.

A summary of the subjects who completed treatment and relapsed (defined as **Relapse_{overall}**) will be prepared displaying the number of subjects relapsing overall and by SVR visit window (within the SVR₄, SVR₁₂, SVR₂₄ windows or after SVR₂₄ window), including the subject number and the SVR visit window corresponding to the first occurrence of relapse. A similar listing will be prepared for subjects who prematurely discontinued treatment and relapsed after having HCV RNA < LLOQ at their Final Treatment Visit.

The number and percentage of subjects who do not achieve SVR_{12} will be summarized by reason for non-response (as defined in Section 10.1). A listing of subject numbers and reason for non-response will be prepared. A similar summary and listing will be prepared for subjects who do not achieve SVR_{24} .

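### One SVR12 sensitivity analysis, presented as imputation of missing values, also counts as cured those early discontinuers whose post-treatment viraemia was observed

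*SAP*

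**What the plan says.** SAP 10.5.1 states its purpose plainly: SVR12 "will be presented using the following other methods to impute missing HCV RNA values". The first method carries forward the last post-baseline value when the SVR12-window value is missing. The second is to "impute as described in Section 6.3 but treat SVR₁₂ non-responders who were categorized as" one of two reasons for non-response as successes. The two reasons are premature discontinuation without on-treatment virologic failure, and missing follow-up data in the SVR12 window.

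Both categories are defined in SAP 10.1, under the reasons for SVR12 non-response. The missing follow-up category (reason 5) is limited to subjects without data in the window after imputation. The early-discontinuation category (reason 3) is not. It takes any "non-responder who prematurely discontinued study drug [study drug duration < 77 days] and did not meet the" on-treatment failure definition.

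The relapse category (reason 2) cannot catch these subjects, because it applies only "for subjects who complete treatment". SAP 10.1 fixes the cut-off: "For the analysis of relapse, completion of treatment is defined as any subject with study drug duration of 77 days or greater". End-of-treatment failure, also in SAP 10.1, needs both a drug duration of at least 36 days and a sample on or after Day 36.

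**The concern.** A sensitivity analysis for missing data should vary the outcomes that are unknown and leave the known ones alone. Here the second method is applied to a category defined by treatment duration, not by missingness, so it can overwrite an observed failure with a success. The error can go only one way, in favour of the drug.

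The plan itself expects such subjects. SAP 10.7 provides a listing of "subjects who prematurely discontinued treatment and relapsed after having HCV RNA < LLOQ" at the final treatment visit. SAP 10.8 names the early-discontinuation category among the subjects whose virus will be sequenced if HCV RNA reaches 1000 IU/mL or more after stopping. The same subject could therefore have rebound virus sequenced and be counted as an SVR12 success in this table. Protocol 5.1.2 and 5.1.3 keep early discontinuers in post-treatment follow-up for 24 weeks, so rebound can be observed.

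At stake is how a reader interprets the spread between the primary and sensitivity rates. Part of that spread could be known failures relabelled, not uncertainty from missing data.

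**Working it through.** **The plan's own figure.** The documents give no figure for this sensitivity analysis. The one design figure nearby is power above 90% (Protocol 8.2, SAP 4.3) with n = 90, true rate 0.96 and threshold 0.86. It reproduces with the null variance:

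- se0 = √(0.86 × 0.14 / 90) = 0.0366
- se1 = √(0.96 × 0.04 / 90) = 0.0207
- power = Φ((0.10 − 1.96 × se0) / se1) = 91.5%

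That figure is not in dispute and does not depend on the rule examined here.

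**Tracing the definitions.** Three hypothetical early discontinuers, each put through SAP 10.1 and then the second method of 10.5.1:

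1. *Stops at Day 50, suppressed at the final treatment visit, then two consecutive post-treatment values ≥ LLOQ.* There is no breakthrough. It is not an end-of-treatment failure, because the final value was < LLOQ. It is not a relapse, because 50 < 77 days. SVR12 is not achieved, because a confirmed quantifiable value exists. The reason is 3, so the subject is counted as a success although failure was observed.
2. *Stops before Day 36, still quantifiable without ever meeting breakthrough, and quantifiable after stopping.* It is not an end-of-treatment failure (fewer than 36 days) and not a relapse (fewer than 77 days, and not suppressed at the final visit). The reason is 3, so the subject is counted as a success although failure was observed.
3. *Stops at Day 50, suppressed, no post-treatment sample.* The window value is missing and SAP 6.3 imputes failure. The reason is 3, so the subject is counted as a success. This is the case that a missing-data method is meant to address.

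Relapse24 does not rescue cases 1 and 2, because it applies only to subjects who achieved SVR12.

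**What is still caught.** Breakthrough is excluded from reason 3. That includes a single breakthrough-level value followed by loss to follow-up, and a breakthrough-level final treatment value confirmed by the next post-treatment sample. End-of-treatment failure from Day 36 is excluded too. The gap is limited to the patterns in cases 1 and 2.

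**Size.** If k subjects follow cases 1 or 2, the sensitivity rate rises by k/90 compared with keeping them as failures:

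- k = 0: 0 points
- k = 1: 1/90 = 1.1 points
- k = 3: 3/90 = 3.3 points

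The range 0 to 3 is an assumption. The documents give no expected number of early discontinuers or of rebounds among them.

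**The case against.** The strongest reply is that nothing is decided on this analysis. The 86% criterion belongs to the primary ITT analysis (Protocol 8.1.2.1, SAP 10.3), where every subject described above is a failure. SAP 10.5.1 only presents results and sets no success rule. The second method also sits beside two less favourable ones: the primary rule, which counts remaining missing data as failure, and the carry-forward method, which leaves observed viraemia in the window as failure. A reader sees the most favourable of three scenarios. The listings in SAP 10.7 (early discontinuers who relapsed, and each subject's reason for non-response) would let a careful reader undo much of the reclassification. All of this stands, and it limits the point to one supportive table. It does not make the rule right: a best-case scenario for missing data still should not replace data that are present.

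One could also argue that stopping early is not a failure of the regimen. That may justify setting such subjects aside, which mITT-GT-VF already does. It does not justify counting documented viraemia as SVR12.

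A reader might infer three stronger things that the documents do not support:

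- *That the rule could turn a failed trial into a successful one.* It cannot. Pass and fail do not exist for this analysis, and the ITT count does not change.
- *That every early discontinuer is relabelled.* Only SVR12 non-responders are. Those who stop early and reach SVR12 are already successes.
- *That mITT-GT-VF must change as well.* The 77-day rule does remove these rebounders from that population. However, Protocol 8.1.2.2 itself limits relapse to subjects with at least 77 days of drug, and Protocol 8.1 builds mITT-GT-VF by excluding non-virologic failures. Changing it would depart from those definitions and reach into the resistance analyses. It is a debatable design choice, not an error.

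**Conclusion.** The point holds for the second method in SAP 10.5.1 and no further. As written, a rule presented as imputation of missing values counts observed post-treatment virologic failure as success for early discontinuers of the two kinds traced above. Each such subject inflates that sensitivity rate by 1.1 points at n = 90. The total depends on a count that the documents do not give and that may be zero. The conclusion rests on reading reason 3 literally, and the contrast with reason 5, which does carry a missing-data condition, supports that reading. The primary analysis and the non-inferiority decision are unaffected.

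**What to change.** Amend the second bullet of SAP 10.5.1 so that a non-responder in the two named categories becomes a success only if both conditions hold:

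- the SVR12-window value is still missing after Section 6.3 imputation; and
- there is no observed post-treatment failure, meaning no confirmed post-treatment HCV RNA ≥ LLOQ and no last available post-treatment value ≥ LLOQ.

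Subjects with either kind of observed failure stay failures regardless of treatment duration. Both criteria come from SAP 10.1: the confirmation rule, and the convention that a quantifiable last value counts as relapse without confirmation. A single unconfirmed value followed by a value < LLOQ does not bar reclassification, which agrees with the SVR12 definition.

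The amended bullet remains a best-case missing-data scenario and does not collapse into the carry-forward method. For example, a subject who stops before Day 36 with a quantifiable last on-treatment value and no later sample is a failure under carry-forward and a success here.

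The cost is a change of SAP wording and one program condition, with no new data. The downside is that this sensitivity rate may be slightly lower.
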